22. Optional Post-Progression Tumor Sample: for subjects who signed a separate ICF, an optional post-progression tumor sample for exploratory biomarker analysis may be collected following disease progression per RECIST v1.1 by local investigator and prior to initiation of subsequent anticancer therapy.
23. AEs: AEs and SAEs (regardless of causality) will be collected from the time of signed informed consent through 30 days following the last dose of study treatment or until initiation of a new anticancer treatment, whichever comes first.

Table 2 ASP1650 Pharmacokinetic and Immunogenicity Schedule

Study Day (1 Cycle = 14 Days)		Time (relative to dosing in each cycle)	Window	ASP1650 Pharmacokinetics Safety Lead-in Phase and all Subjects from Simon Stage I of Phase 2	ASP1650 Pharmacokinetics Simon Stage II of Phase 2	ASP1650 Immuno- genicity
Screening						
Cycles 1	Day 1	Predose (0 hr)	within 60 minutes prior to dosing	X	X	X
		1.5 hrs after start of infusion	± 15 minutes	X		
		Immediately after end of infusion	within 10 minutes after the end of the infusion	X	X	
		0.5 hr after end of infusion	± 5 minutes	X		
		1.5 hrs after end of infusion	± 15 minutes	X		
		3 hrs after end of infusion	± 15 minutes	X		
		6 hrs after end of infusion	± 30 minutes	X		
		24 hrs after end of infusion	± 120 minutes	X		
		48 hrs after end of infusion	± 120 minutes	X		
		72 hrs after end of infusion	± 120 minutes	X		
Cycle 2	Day 1	Predose (0 hr)	within 60 minutes prior to dosing	X	X	
Cycle 3	Day 1	Predose (0 hr)	within 60 minutes prior to dosing	X	X	
		1.5 hrs after start of infusion	± 15 minutes	X		
		Immediately after end of infusion	within 10 minutes after the end of the infusion	X	X	
		0.5 hr after end of infusion	± 5 minutes	X		
		1.5 hrs after end of infusion	± 15 minutes	X		
		3 hrs after end of infusion	± 15 minutes	X		
		6 hrs after end of infusion	± 30 minutes	X		
		24 hrs after end of infusion	± 120 minutes	X		
		48 hrs after end of infusion	± 120 minutes	X		
		72 hrs after end of infusion	± 120 minutes	X		
Cycle 4	Day 1	Predose (0 hr)	within 60 minutes prior to dosing	X	X	
Cycle 5	Day 1	Predose (0 hr)	within 60 minutes prior to dosing	X	X	X
Cycles 6 to 8	Day 1	Predose (0 hr)	within 60 minutes prior to dosing	X	X	
Cycle 9	Day 1	Predose (0 hr)	within 60 minutes prior to dosing	X	X	X
Cycles 10 to 12	Day 1	Predose (0 hr)	within 60 minutes prior to dosing	X	X	
Study Treatment Discontinuation Visit				X		X
30-day Safety Follow-up Visit				X		X

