5.5 Adverse Events and Other Safety Aspects

5.5.1 Definition of Adverse Events

An AE is any untoward medical occurrence in a subject administered a study drug, and that does not necessarily have to have a causal relationship with this treatment. An AE can therefore be any unfavorable and unintended sign (including an abnormal laboratory finding), symptom, or disease (new or exacerbated) temporally associated with the use of a medicinal product whether or not considered related to the medicinal product.

In order to identify any events that may be associated with study procedures and could lead to a change in the conduct of the study, Astellas collects AEs even if the subject has not received study drug treatment. AE collection begins after the signing of the informed consent and will be collected until 30 days after the last dose of study drug or the subject is determined to be a screen failure.

Care will be taken not to introduce bias when detecting AEs and/or serious adverse events (SAEs). Open-ended and non-leading verbal questioning of the subject is the preferred method to inquire about AE occurrences.

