5.5.1.3 Disease Progression and Study Endpoints

Under this protocol, the following event(s) will not be considered as an(S)AE:

- Disease Progression: events including defined study endpoints that are clearly consistent with the expected pattern of progression of the underlying disease are not to be recorded as AEs. These data will be captured as efficacy assessment data as outlined in [Section 5.3 Efficacy and Immunogenicity Assessments]. If there is any uncertainty as to whether an event is due to anticipated disease progression and/or if there is evidence suggesting a causal relationship between the study drug and the event, it should be reported as an (S)AE. All deaths up to 30 days after the last dose of study drug must be reported as an SAE, even if attributed to disease progression.
- Disease progression can be considered as the worsening of a subject's condition attributable to germ cell tumor. It may be an increase in the severity of the disease under study and/or increases in the symptoms of the disease. The development of new, or progression of existing metastases to the primary cancer under study should be considered as disease progression not an AE. Events which are unequivocally due to disease progression should not be reported as an AE during the study
- Pre-planned and elective hospitalizations or procedures for diagnostic, therapeutic, or surgical procedures for a pre-existing condition that did not worsen during the course of the clinical trial. These procedures are collected per the eCRFs Completion Guidelines.

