5.5.5 Reporting of Serious Adverse Events (SAEs)

The collection of AEs and the expedited reporting of SAEs will start following receipt of the informed consent and will continue until 30 days) after the last dose of study drug or the subject is determined to be a screen failure.

In the case of a SAE, the investigator must contact the sponsor by fax or email immediately (within 24 hours of awareness).

The investigator must complete and submit an SAE worksheet containing all information that is required by local and/or regional regulations to the sponsor by email or fax immediately (within 24 hours of awareness).

The SAE worksheet must be signed by a medically qualified investigator (as identified on Delegation of Authority Log). Signature confirms accuracy and completeness of the SAE data as well as the investigator causality assessment including the explanation for the causality assessment.

For contact details, see [Section II Contact Details of Key Sponsor's Personnel]. Fax or email the SAE/special situations worksheet to:

Astellas Pharma Global Development – United States
Pharmacovigilance
[contact]
Email: [contact]

If there are any questions, or if clarification is needed regarding the SAE, please contact the sponsor's medical monitor/study physician or his/her designee [Section II Contact Details of Key Sponsor's Personnel].

Follow-up information for the event should be sent promptly (within 7 days of the initial notification).

Full details of the SAE should be recorded on the medical records, SAE/special situation worksheet and on the eCRF.

The following minimum information is required:

- International Study Number (ISN)/Study number,
- Subject number, sex and age,
- The date of report,
- A description of the SAE (event, seriousness criteria),
- Causal relationship to the study drug (including reason), and
- The drug provided (if any)

The sponsor or sponsor's designee will medically evaluate the SAE and determine if the report meets the requirements for expedited reporting based on seriousness, causality, and expectedness of the events (e.g., suspected unexpected serious adverse reaction (SUSAR) reporting) according to current local/regional regulatory requirements in participating countries. The sponsor or sponsor's designee will submit expedited safety reports (e.g.,

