7.5.2 Adverse Events

AEs will be coded using the MedDRA.

TEAE is defined as an AE observed after starting administration of the study drug and up to 30 days after the last dose of study drug.

The number and percentage of subjects with treatment-emergent AEs, SAEs, AEs leading to withdrawal of treatment, and AEs related to study drug will be summarized by System Organ

Class, preferred term, cohort and dose level. The number and percentage of AEs by severity will also be summarized. All AEs will be listed.

A study drug-related TEAE is defined as any TEAE with a causal relationship of YES by the investigator.

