5.3.1.2 Treatment-Emergent Adverse Events

Treatment-emergent adverse events (TEAEs; frequency, severity, seriousness, and relationship to study drug).

TEAE is defined as an adverse event observed after starting administration of the study drug, and up to 30 days after the last dose of study drug. If the adverse event occurs on Day 1 and the onset check box is marked “Onset after first dose of study drug” or the onset check box is left blank, then the adverse event will be considered treatment-emergent. If the adverse event occurs on Day 1 and the onset check box is marked “Onset before first dose of study drug”, then the adverse event will not be considered treatment-emergent. If a subject experiences an event both during the preinvestigational period and during the investigational period, the event will be considered as TEAE only if it has worsened in severity (i.e. it is reported with a new start date). All adverse events collected that begin within 30 days after taking the last dose of study drug will also be counted as TEAE. Any AEs with onset dates completely missing will be considered TEAEs in summaries. AEs with partially missing onset dates will be assumed TEAEs unless the available portion of the date indicates that the onset was strictly before start of study medication.

A drug-related TEAE is defined as any TEAE with at least possible relationship (possibly or probably related) to study treatment as assessed by the investigator or with missing assessment of the causal relationship

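### Table 1 footnote 23 ends AE and SAE collection at new anticancer treatment, while Protocol 5.5.1, 5.5.5 and both TEAE definitions run to 30 days after the last dose

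*Protocol*

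**What the plan says.** Two end points for AE collection stand in the current protocol.

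- **Table 1, footnote 23** (attached to the AE row) covers AEs and SAEs whatever their causality, from consent to 30 days after the last dose "or until initiation of a new anticancer treatment, whichever comes first".
- **Section 5.5.1** says that AEs "will be collected until 30 days after the last dose of study drug or the subject is determined to be a screen failure".
- **Section 5.5.5** ends AE collection and expedited SAE reporting at 30 days "after the last dose of study drug or the subject is determined to be a screen failure".

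The analysis rules use the longer window. Protocol 7.5.2 defines a TEAE as an AE "observed after starting administration of the study drug and up to 30 days after the last dose of study drug". SAP 5.3.1.2 adds: "All adverse events collected that begin within 30 days after taking the last dose of study drug will also be counted as TEAE". Neither mentions new anticancer treatment.

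Two further provisions limit the consequences. Section 5.5.1.3 states: "All deaths up to 30 days after the last dose of study drug must be reported as an SAE", including deaths attributed to progression. Section 5.5.6 requires prompt notification of any AE or SAE learned of after the collection period that the investigator thinks may be related to study drug or study participation. It refers to Section 5.5.1 for the definition of that period.

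**The concern.** Sites tend to work from the Schedule of Assessments, while the tables are programmed from the TEAE definition. Here the two disagree about the last part of the window. If a subject starts another anticancer treatment before day 30, a site applying footnote 23 stops recording, while a site applying 5.5.1 continues. The SAP can count only what was collected, so it cannot recover the difference.

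Safety and tolerability is a secondary endpoint, and the 1500 mg/m² target exceeds the highest dose in the phase 1 study (1000 mg/m²). What is at stake is whether the TEAE and SAE tables contain what their definition says they contain. Starting another antitumor treatment is a listed reason for stopping study drug (Section 6.1), and the SAP plans a summary of new anticancer therapy (6.2.4.5), so the situation is foreseeable.

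**Working it through.** The plan gives no figure to reproduce, so the check is a comparison of texts.

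**1. The windows side by side**

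| Place | Purpose | End of window | Stops at new anticancer treatment? |
|---|---|---|---|
| Protocol Table 1, footnote 23 | AE and SAE collection | 30 days after last dose, or new treatment if earlier | Yes |
| Protocol 5.5.1 | AE collection | 30 days after last dose, or screen failure | No |
| Protocol 5.5.5 | AE collection and SAE reporting | 30 days after last dose, or screen failure | No |
| Protocol 5.5.1.3 | Deaths reported as SAEs | 30 days after last dose | No |
| Protocol 7.5.2 | TEAE definition | 30 days after last dose | No |
| SAP 5.3.1.2 | TEAE definition, collected events | 30 days after last dose | No |

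Footnote 23 is the only one with the earlier stop.

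**2. Who is affected.** For a subject who starts no new treatment, or starts it on day 30 or later, the rules coincide. They diverge only for a start before day 30.

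**3. Which events are exposed.** Among events beginning between the new treatment and day 30:

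- Deaths are covered by 5.5.1.3.
- Possibly related AEs and SAEs are covered by 5.5.6. Read literally, its trigger is the end of the 5.5.1 period, which is day 30. I take it as also catching such events earlier, which is the reading most favourable to the plan.
- Non-fatal events not judged related, including non-fatal SAEs, have no second route to the database under footnote 23.

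**4. What the tables do.** AE tables count subjects, not events or person-time (SAP 6.5.2). The safety set keeps everyone with at least one dose (SAP 4.2). An unrecorded event can therefore remove a subject from a numerator but never from the denominator. It changes a row only if the subject has no other qualifying event in that row.

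**5. Illustration for one subject.** Let new treatment start d days after the last dose. Footnote 23 then drops 30 − d of the 30 post-dose days. The values of d are assumptions, because the documents give none.

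| d (assumed) | Days dropped | Share of the 30 days |
|---|---|---|
| 7 | 30 − 7 = 23 | 23/30 = 77% |
| 14 | 30 − 14 = 16 | 16/30 = 53% |
| 21 | 30 − 21 = 9 | 9/30 = 30% |
| 30 or more, or never | 0 | 0% |

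These are shares of one subject's post-dose window. They do not estimate the error in any AE percentage, which also depends on how many subjects start early, which rule their site follows, and how many exposed events occur. None of these is given. For scale only, one subject missing from a row changes its percentage by 1/46 = 2.2 points at the planned maximum of 46 subjects, and by more in tables split by dose level.

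**The case against.** The strongest reply is that the protocol already indicates which rule governs. Section 5.5.6 names 5.5.1 as the place where the collection period is defined, and 5.5.5, the deaths rule and both TEAE definitions agree with it. Footnote 23 is then a stray line. Every subject is also due a 30-day safety visit with the AE row marked, and footnote 4 exempts nobody on new therapy. Deaths and possibly related events are covered in any case.

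Most of this stands, and it narrows the point. It does not remove it. The cross-reference in 5.5.6 is incidental and does not say that 5.5.1 overrides the schedule. The AE row at the 30-day visit carries footnote 23, so a site could hold the visit and still properly believe that events starting after new treatment are not to be recorded.

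A second reply is that a shorter window is a respectable choice, because events after another agent are confounded by that agent. That is fair, but the TEAE definitions then need the same cut.

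A reader might go further and infer that early switching is common here, so that AE rates are biased downward. The documents do not support this. They give no timing for subsequent therapy. The population is one with no standard treatment or ineligible for it (Section 3.1), and subjects may stay on study drug after progression, up to 12 cycles (Section 6.1). Both argue against assuming rapid switching.

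**Conclusion.** The contradiction is real and in current text, and its reach is small. It concerns subjects who start new anticancer treatment before day 30 and, among their late events, non-fatal ones, mainly those not judged related. For these, footnote 23 permits non-collection of events that the TEAE tables are defined to include, while the subject remains in the denominator. The number of subjects is unknown, so no effect on a TEAE or SAE percentage can be stated.

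Three stronger readings are not supported:

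- That the analysis credits uncollected days as event-free observation: no person-time or exposure-adjusted AE rate is planned.
- That collection differs between sites: this is possible under two conflicting rules, but not shown.
- That expedited reporting of drug-related events is lost: sponsor submission turns partly on causality (5.5.5), and 5.5.6 still calls for notification of possibly related events.

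The confirmed ORR and the Simon stage decision do not depend on this window. The conclusion rests on reading footnote 23 as an operative instruction to sites and 5.5.6 as catching possibly related events throughout.

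**What to change.** Reconcile the passages to one collection end. Since 5.5.6 already points to 5.5.1, the simplest route is to amend footnote 23 so that it agrees with 5.5.1 and 5.5.5 (30 days after the last dose, or screen failure). Add a flag for AEs starting on or after the first date of new anticancer treatment, and state in SAP 5.3.1.2 and 6.5.2 that TEAE tables will be shown with and without the flagged events. This answers the confounding argument without discarding data.

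If the shorter window is what the sponsor intends, amend 5.5.1, 5.5.5 and both TEAE definitions (Protocol 7.5.2, SAP 5.3.1.2) to match. Section 5.5.6 should then refer to the revised period, and the separate 30-day rule for deaths should be stated as an exception.

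The first route costs one footnote, one AE flag and slightly more AE entry after new therapy.

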1 INTRODUCTION

Germ-cell tumors (GCTs) in male subjects are cancerous tumors derived from germ cells normally occurring inside the testicles and represent the most common solid tumor type in men between age 15 and 35 years [Einhorn, 1997]. An estimated 9,310 new cases of testicular germ cell cancer [Surveillance, Epidemiology, and End Results, 2017] will be diagnosed in the United States in 2018, including an estimated 4910 cases of pure seminomas and 4400 cases of nonseminomas. Pure seminomas are more sensitive to radiation while nonseminomas tend to grow and spread more quickly. A testicular tumor that contains both pure seminoma and nonseminoma cells is treated as a nonseminoma [National Cancer Institute, 2018].

Germ-cell tumors are remarkably chemosensitive with up to 80% of subjects with metastatic disease achieving cure with cisplatin-based combination chemotherapy [Adra et al, 2018; Hanna, 2014].

Subjects with tumors that relapse or progress after initial chemotherapy may be cured with salvage therapy including salvage surgery, standard dose chemotherapy, or high-dose chemotherapy plus peripheral-blood stem-cell transplant (PBSCT) [Adra et al, 2018; Feldman et al, 2010; Einhorn et al, 2007; Kondagunta et al, 2005; Loehrer et al, 1998; Murphy et al, 1993; Loehrer et al, 1986]. Despite these positive results with cisplatin-based front-line and salvage chemotherapy regimens and high dose chemotherapy with PBSCT, approximately 15% of GCT subjects are currently incurable and represent a subset of subjects with poor prognosis that are likely incurable with current available therapeutic options [Hartmann et al, 2001, Pont et al, 1997; Saxman et al, 1994]. Recently, a phase 2 trial of the immune checkpoint inhibitor pembrolizumab did not show any clinically meaningful single-agent activity (no partial or complete responses [CR]) in subjects with platinum refractory germ-cell tumors [Adra et al, 2018]. Therefore, a significant unmet medical need exists for these male subjects with incurable platinum refractory germ cell tumors. ASP1650 (IMAB027) is being developed with the goal of addressing this unmet medical need.

1.1 Background

ASP1650 is a novel chimeric mouse/human IgG1 antibody directed against the tumor-specific protein CLDN6, a primitive tight junction protein. The target is a member of the claudin family of more than 20 structurally related proteins that are involved in the formation of tight junctions in epithelia and endothelia [Niimi et al, 2001]. Tight junctions, together with adherens junctions and desmosomes, form the apical junctional complex in epithelial and endothelial cellular sheets. Adherens junctions and desmosomes are responsible for the mechanical adhesion between adjacent cells, whereas tight junctions are essential for the tight sealing of the cellular sheets forming a luminary barrier and controlling the paracellular ion flux.

CLDN6 expression is restricted to the embryo-fetal stage in humans and is virtually absent from any normal adult human tissue. However, it is frequently aberrantly expressed in various cancers of high medical need, including 93% of testicular, 56% of ovarian, and 23%

of uterine cancer tissue samples. In testicular cancer tissue samples, CLDN6 was expressed in 93% of seminomas and 95% of nonseminomas with > 65% of cases having > 80% of tumor cells expressing CLDN6. In ovarian cancer, CLDN6 expression is more frequent in prognostically worse settings (expression in higher International Federation of Gynecology and Obstetrics stage, metastatic lesions, less differentiated high-grade cancer cells).

This study is evaluating this first-in-class investigational drug, ASP1650, as a potential treatment for male subjects with incurable platinum refractory germ cell tumors.

1.2 Nonclinical and Clinical Data

1.2.1 Nonclinical Data

ASP1650 induced antibody-dependent cell-mediated cytotoxicity (ADCC) and complement-dependent cytotoxicity (CDC) in testicular cancer cell lines expressing human CLDN6. ASP1650-directed cell killing was strictly dependent on the presence of CLDN6 and did not act via non-specific immune activation. In in vivo assessments, ASP1650 significantly inhibited testicular tumor growth in an immunocompromised xenografted mouse model. A combination of ASP1650 with platinum derivatives demonstrated a more potent antitumor effect than ASP1650 or chemotherapy alone.

CLDN6 is a cancer-specific antigen not expressed in normal adult human tissues and therefore, there is no specific target organ for testing of on-target toxicity. Cynomolgus monkeys were chosen as a non-rodent species to assess the effects of ASP1650 due to a CLDN6 tissue distribution and CLDN6 molecular sequence that was similar to humans. Also, the binding affinity of ASP1650 to cynomolgus and human orthologs of CLDN6 is identical and ASP1650-induced immune effector functions (ADCC, CDC) are comparable between both species.

Limited toxicological endpoints were studied in mice as this species was considered less predictive for testing whether ASP1650 might affect human safety due to CLDN6 expression in mouse pancreas, thyroid, and placenta and lower overall sequence homology between mouse and human compared to homology between cynomolgus monkey and human. Furthermore, the binding affinity of ASP1650 to the mouse ortholog is 10-fold lower compared to human CLDN6 and ASP1650-induced immune effector functions (ADCC, CDC) differ between mice and humans.

Safety pharmacology and toxicity of ASP1650 were assessed in 1 single ascending dose study in cynomolgus monkeys (intravenous administration, up to 100 mg/kg), one 29-day repeated dose study in mice (weekly intravenous administration of ASP1650 at doses up to 400 mg/kg). No target organs of toxicity were identified in these studies.

Two tissue cross-reactivity studies were conducted using human tissues. The results showed that ASP1650 did not bind to any normal adult human tissues except for intercalated duct cells of the pancreas (in 1 of 3 donors) and blood platelets (in all 3 donors).

Please refer to the current Investigator's Brochure (IB) for most recent nonclinical data.

